Subjects treated for diabetes or suffering from chronic renal failure or hepatic insufficiency or chronic heart failure will be excluded from the study. Also, because of the known effects of steroids on sleep, subjects on those medications will be excluded from the study. A family history of diabetes will be recorded during the medical history and physical examination and controlled within our analyses. Also, the potential effects of other medications or substances, such as alcohol or smoking, will be controlled within our analyses. Subjects with a diagnosis of substance abuse or dependence will be excluded from the study due to the potential effects of these substances on sleep and metabolism. Patients should be free of hypnotic use or sedative antidepressants administered at bedtime to improve sleep for one month before entering the study. Finally, patients using psychotropic medications, i.e., SSRI, who do not meet the criteria for a current major psychiatric disorder, and have continuous complaints of insomnia, will be included in the study. This is because a large portion of insomniacs consist of depressed individuals whose depression improved but still they have complaints of chronic insomnia. Potential confounding effects of medication on some of the outcome measures, i.e., objective sleep duration, will be dealt with in the analysis

Women and Minority Inclusion – In this project, we will include middle-aged men and women 30- 60 because they represent the majority of patients with insomnia in the general and clinic population. Women who are pregnant or breastfeeding will not be enrolled in the study. We plan to recruit about 21% of subjects belonging in minority groups. The racial and ethnic distribution shown in the Targeted/Planned Enrollment Table reflects the general demographics of our region. Minorities will be recruited from our clinics as well as through advertisements in papers with large groups of minority readers, such as Harrisburg, PA and Lebanon, PA.

IRB Protocol No. 35933
Version Date: 11/10/2015

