The very first item of the agenda is to review the sleep diary for the previous week. This provides a clear message to the patient that self-monitoring is expected and is an essential component of therapy. The next step is to check the extent to which the patient has complied with previous recommendations. After problem solving adherence issues, a new treatment component is introduced. Each procedure is described along with its rationale and objectives. Handouts will always be provided to consolidate the new information presented during the session. The final item on the agenda is to review homework assignment for the upcoming week giving a written summary to the patient.

The **trazodone group** will receive a standard handout on sleep hygiene instructions and subsequent biweekly and monthly visits to check treatment effectiveness, adherence and possible side-effects, if they occur, and also follow-up review of sleep hygiene practices. All patients will receive a standard dose of trazodone 50 mg. in their first visit and will be followed-up with 2 additional biweekly visits. During these biweekly visits, doses will be adjusted according to drug effectiveness and possible side-effects. Consecutive visits will be scheduled monthly and will focus on assessing treatment effectiveness, adherence and possible side-effects and need to adjust medication doses.

Techniques

1. Medical History and Physical Examination

Each subject will have a complete medical history and physical examination using a semi-structured format and a battery of clinical tests, including complete blood count, liver function test, urinalysis, lipid panel, thyroid indexes, and electrocardiography. Pre-menopausal women will also have a pregnancy test performed. Blood pressure will be measured in the morning and in the evening using a pneumoelectric microprocessor-controlled instrument. The recorded blood pressure will be the average of 3 consecutive readings during a 5-minute period following 10 minutes of rest in the supine position. Anthropometric measures will include height, weight, neck size, and waist and hip measurements according to standard procedures. Specifically, neck size is measured at the superior border of the cricothyroid membrane with the subject in the upright position. Waist is measured at or 1 cm above the umbilical midline and hip at the widest area around the buttocks.

2. Objective assessment of Nighttime Sleep

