a. Polysomnography – Each subject will be monitored continuously for eight hours for 2 consecutive nights (adaptation night and one baseline night) according to standard techniques (Rechtschaffen A, Kales A, 1968). Also, to improve the accuracy and reliability of our nighttime sleep measures, the subjects' typical sleep time at home will be assessed objectively via actigraphy for two weeks before the sleep laboratory recordings (see below) and during the sleep lab recordings. Respiration will be monitored throughout the night by thermocouples at the nose and mouth (Salter Labs) and nasal cannula/pressure and by thoracic strain gauges. We will use both thermocouples and nasal cannula because it has been reported that the pressure signal identifies transient elevated upper airway resistance not detected conventionally (Iber et al, 2007). An apnea/hypopnea index ≥ 5 will be used to define the presence of sleep apnea.

b. Actigraphy – An actigraphy monitor (ActiGraph GT3X) will be placed on the wrist of the nondominant hand of subjects. The subjects will be asked to keep an actigraphy log for two week periods in which they note daily time to bed, time out of bed, or times when the device is removed (e.g., taking a bath, swimming).

3. Subjective assessment of Nighttime Sleep and Arousal

a. Post-sleep Assessment – Throughout the study, subjects will complete a post-sleep questionnaire upon awakening each morning in the sleep lab and will estimate time to fall asleep, number of nightly awakenings, total sleep time, soundness and quality of sleep, and morning sleepiness.

b. Sleep Diary – A 2-week sleep log or diary will be used for assessment of the subjects' perceived sleep patterns at the screening phase, at the onset of the study, during the intervention period, at the end of the intervention and at follow-up.

c. Sleep Quality – The Pittsburg Sleep Quality Index (PSQI) will be used for assessment of the subjects' overall sleep quality at the onset of the study, at the end of the intervention and at follow-up (Buysse et al, 1989).

d. Insomnia Severity – The Insomnia Severity Index (ISI) will be used for assessment of the subjects' overall perceived insomnia severity at the onset of the study, during the intervention period, at the end of the intervention and at follow-up (Bastien et al, 2001).

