4. There are a few potential risks associated with trazodone. Trazodone is a sedative triazolopyridine antidepressant, habitually used for the treatment of depression and insomnia because it possesses antidepressant and also anxiolytic and hypnotic activities (Al-Yassiri et al, 1981; McCall, 2010). Pharmacologically, it is a serotonin antagonist and reuptake inhibitor; it is a blocker of postsynaptic serotonin receptors 5-HT_{1A}, 5-HT_{1C}, and 5-HT₂, as well as postsynaptic α ₁-adrenergic receptors. It has a peak serum concentration of 1-2 hours and an elimination half-life of about 5-9 hours. When prescribed as an antidepressant, i.e., to alleviate major depression, the usual doses of trazodone are \geq 150 mg daily. Daytime doses of trazodone at 100 mg have been found to impair critical flicker fusion and choice reaction time 1-4 hours later in only two studies (Burns et al, 1986; Warrington et al, 1984). Bedtime doses of trazodone at 100 mg have been found to lower blood pressure and impair critical flicker fusion the next morning in one study (Saletu-Zyhlarz et al, 2001). One study mentioned in a recent review found orthostatic hypotension and priapism as a side effect of bedtime trazodone administration (James and Mendelson, 2004). When prescribed as a hypnotic, it is habitually used at low-doses (i.e., 50 mg daily at bedtime). The vast majority of studies have shown that trazodone improves subjective sleep quality and increases objective total sleep time, percent of stages 3 and 4, and sleep efficiency, and decreases the percent of stage 1, number of awakenings, and stage shifts, as assessed by PSG (Burns et al, 1986; Saletu-Zyhlarz et al, 2001; James and Mendelson, 2004; Dording et al, 2002; Nierenberg et al, 1994; Haffmans, 1999; Walsh et al, 1998; Montgomery et al, 1983; Yamadera et al, 1998; Ware and Pittard, 1990; Kaynak et al, 2004; Zavesicka et al, 2008). There are no controlled studies or clinical reports of major side-effects with low-dose trazodone when administered at bedtime in insomniacs. The most common side effect of low-dose trazodone when administered at bedtime may be minimal morning sedation, based on clinical experience. Common risks of trazodone given at higher doses include headache, dry mouth, blurred vision, dizziness, fatigue, nausea and suicidal thoughts in children, adolescents and young adults with depression.

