11.0 Statistical Analysis of the Study

Analysis

a. Sample Size Calculation – This is a pilot study to collect preliminary data using two interventions, i.e., trazodone or CBT, with unknown effects for chronic insomnia with objective short sleep duration. Based on our previous experience with interventional studies, we suggest that 10 subjects per group will be adequate to detect a difference of 20 minutes in objective sleep duration between the two treatment interventions. To allow for an anticipated 20% attrition rate, 24 subjects will be assigned to a study intervention to ensure complete data from 20 participants. The results of this study will allow the establishment of sample size for any future studies. Our statistical consultant in this study is [name].

b. Analytic Plan

Specific Aim 1: Examine the Effect of Trazodone vs. CBT for the Primary Outcome Variables (objective and subjective sleep duration) in Patients with Chronic Insomnia with Objective Short sleep Duration

Throughout the analysis, we will compare the differences (end of the interventional study baseline) between the two groups of the outcome of interest (e.g., total sleep time).

Total Sleep Time, Polysomnography: Both at baseline and the end of the intervention, polysomnography will be measured for 2 consecutive nights. We will calculate the time-specific difference from the baseline to the end of intervention. Then, we will compare the two treatment conditions with respect to the overall mean change across all time points (“difference of difference”) using the two-sample t-test. Alternatively, repeated measures analysis of variance (ANOVA) will be used to compare treatment conditions with respect to polysomnographic total sleep time changes from baseline. The time and treatment condition main effects as well as interaction between time and treatment condition will be tested. Adjustments for multiple comparisons across different time points and between intervention groups will be performed. Potential confounders and interaction between treatment condition and confounder will also be examined. In the event that the distribution of polysomnographic total sleep time are not consistent with the assumptions of normality required for ANOVA, attempts will be made to find suitable transformation.

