Total Sleep Time, Actigraphy: Both at baseline and the end of the intervention, actigraphy will be measured for 2 weeks. We will calculate the time-specific difference from the baseline to the end of intervention. Then, we will compare the two treatment conditions with respect to the overall mean change across all time points (“difference of difference”) using the two-sample t-test. Alternatively, repeated measures analysis of variance (ANOVA) will be used to compare treatment conditions with respect to actigraphic total sleep time changes from baseline. The time and treatment condition main effects as well as interaction between time and treatment condition will be tested. Adjustments for multiple comparisons across different time points and between intervention groups will be performed. Potential confounders and interaction between treatment condition and confounder will also be examined. In the event that the distribution of actigraphic total sleep time are not consistent with the assumptions of normality required for ANOVA, attempts will be made to find suitable transformation.

Total Sleep Time, sleep diary: Both at baseline and the end of the intervention, subjective sleep duration will be measured with a 2-week sleep log. We will calculate the time-specific difference from the baseline to the end of intervention. Then, we will compare the two treatment conditions with respect to the overall mean change across all time points (“difference of difference”) using the two-sample t-test. Alternatively, repeated measures analysis of variance (ANOVA) will be used to compare treatment conditions with respect to subjective total sleep time changes from baseline. The time and treatment condition main effects as well as interaction between time and treatment

condition will be tested. Adjustments for multiple comparisons across different time points and between intervention groups will be performed. Potential confounders and interaction between treatment condition and confounder will also be examined. In the event that the distribution of subjective total sleep time are not consistent with the assumptions of normality required for ANOVA, attempts will be made to find suitable transformation.

Specific Aim 2: Examine the Effect of Trazodone vs. CBT on the Secondary Outcome Variables (insomnia severity, daytime functioning, stress, inflammation and insulin sensitivity) in Patients with Chronic Insomnia with Objective Short sleep Duration

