Subjective sleep quality and insomnia severity: Both at baseline and the end of the intervention, self-reported sleep quality (PSQI) and insomnia severity (ISI) will be measured. We will calculate the time-specific difference from the baseline to the end of intervention. Then, we will compare the two treatment conditions with respect to the overall mean change across all time points (“difference of difference”) using multivariate repeated measures analysis of variance (MANOVA) to compare treatment conditions with respect to all measures of subjective sleep quality and insomnia severity changes from baseline. The time and treatment condition main effects as well as interaction between time and treatment condition will be tested. Adjustments for multiple comparisons across different time points and between intervention groups will be performed. Potential confounders and interaction between treatment condition and confounder will also be examined. In the event that the distribution of subjective sleep quality and insomnia severity measures are not consistent with the assumptions of normality required for MANOVA, attempts will be made to find suitable transformation.

Sleepiness, fatigue, and mood: Both at baseline and the end of the intervention, self-reported sleepiness (ESS), fatigue (POMS-F and MFI) and mood (BDI-II, BAI, and HAD-S) will be measured. We will calculate the time-specific difference from the baseline to the end of intervention. Then, we will compare the two treatment conditions with respect to the overall mean change across all time points (“difference of difference”) using multivariate repeated measures analysis of variance (MANOVA) to compare treatment conditions with respect to all measures of sleepiness, fatigue, and mood changes from baseline. The time and treatment condition main effects as well as interaction between time and treatment condition will be tested. Adjustments for multiple comparisons across different time points and between intervention groups will be performed. Potential confounders and interaction between treatment condition and confounder will also be examined. In the event that the distribution of sleepiness, fatigue, and mood measures are not consistent with the assumptions of normality required for MANOVA, attempts will be made to find suitable transformation.

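### The PSQI is compared between a sleep-drug arm and a no-drug arm with no scoring rule; if its total counts sleep-medicine use, this secondary comparison is biased against trazodone

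*Combined protocol and SAP*

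**What the plan says.** All references are to the combined protocol and SAP.

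- **Instrument.** Section 6.0, Techniques, item 3c: "The Pittsburg Sleep Quality Index (PSQI) will be used for assessment of the" patients' general quality of sleep. Table 3 schedules it for baseline, 3 months and 9 months. Components, item scoring and score range are not given.
- **Analysis.** Section 11.0, Specific Aim 2: at baseline and end of intervention "self-reported sleep quality (PSQI) and insomnia severity (ISI) will be measured". The changes in the two scales are compared between arms together, by repeated-measures MANOVA. The text does not say whether the PSQI total or its components are used, and no item is excluded or analysed separately.
- **Tier.** Section 11.0 lists objective and subjective sleep duration as primary (polysomnography, actigraphy, sleep diary). The PSQI is analysed under the secondary aim.
- **Before entry.** Section 4.0: "Patients should be free of hypnotic use or sedative antidepressants administered at bedtime to improve sleep for one month before entering the study".
- **On study.** Section 6.0, for the trazodone group: "All patients will receive a standard dose of trazodone 50 mg. in their first visit", with later visits that check adherence. The CBT programme in the same section contains no drug.

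**The concern.** A scale item that counts sleep-medicine use measures the assigned treatment as well as the patient's sleep. The washout would put such an item near its minimum in both arms at baseline. It would then rise in the arm told to take a sleep medicine and, if CBT patients use none, stay put in the other. Randomisation does not remove this, because the rise happens after allocation and because of it. Subtracting baseline does not remove it either, because it sits in the change score. The planned transformation for non-normality does not address it.

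Two results could mislead. A real trazodone benefit on the PSQI could be reduced or cancelled, or CBT could look better when sleep quality is the same. The PSQI is also one of only two measures in the joint test of subjective sleep quality and insomnia severity, and that test has no direction. A shift in the PSQI alone could therefore make the joint result significant.

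**Working it through.** **The plan's own figures.** There is no PSQI effect size, SD or power statement to reproduce. Section 11.0 gives 10 per group, for a 20-minute difference in objective sleep duration, without an SD, significance level or power. Only the 10 per group is carried forward, as the number of completers.

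**Inputs**

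| Input | Value | Source |
|---|---|---|
| Completers per arm, n | 10 | Section 11.0 |
| Shift in PSQI change from assigned medicine use, δ | 0 to 3 points | Assumption: one component scored 0 to 3 within the total |
| SD of PSQI change | 3 to 4 points | Assumption |
| Correlation of PSQI and ISI changes, ρ | 0.3 to 0.6 | Assumption |
| Test level | two-sided 0.05, unadjusted | Assumption; not stated in Section 11.0 |
| True difference in sleep quality | none, unless stated | Scenario |

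**Step 1: PSQI alone, two-sample t-test.** The noncentrality is δ / (SD × √(2/10)), with 18 degrees of freedom and critical value 2.101. For δ = 3 and SD = 3 it is 3 / (3 × 0.447) = 2.24. The chance of a significant result is:

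| Shift | SD 3 | SD 3.5 | SD 4 |
|---|---|---|---|
| 0 points | 5% | 5% | 5% |
| 1 point | 11% | 9% | 8% |
| 2 points | 29% | 23% | 19% |
| 3 points | 56% | 44% | 36% |

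Nearly all of the excess is in the direction favouring CBT. At 1 point, that direction accounts for 10.5% at SD 3 and 7.6% at SD 4, against 2.5% with no shift.

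**Step 2: joint PSQI and ISI test.** Taking one change per measure, the two-group MANOVA is a Hotelling T² test. With only the PSQI shifted, D² = (δ/SD)² / (1 − ρ²) and λ = (10 × 10 / 20) × D² = 5D², referred to F(2, 17). At δ = 3:

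| | ρ = 0.3 | ρ = 0.6 |
|---|---|---|
| SD 3 | D² = 1.10, λ = 5.5, rejects 47% | D² = 1.56, λ = 7.8, rejects 62% |
| SD 4 | D² = 0.62, λ = 3.1, rejects 28% | D² = 0.88, λ = 4.4, rejects 39% |

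**Step 3: a real benefit masked.** Suppose trazodone is truly 3 points better on the remaining items, with SD 3. The net difference is 3 − δ. The chance of a significant result favouring trazodone falls from 56% with no shift to 29%, 11% and 2.5% for shifts of 1, 2 and 3 points.

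**Step 4: after the fix.** Without the medicine-use component, δ = 0 by definition and the rejection rate under no difference returns to 5%.

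**The case against.** The strongest objection is that the decisive premise is not in the documents. They name and cite the PSQI but do not say that it has a medicine-use component, how that component scores, or that the total is what will be analysed. This stands as a limit on certainty: the premise is an assumption and use of the total is inferred from the reference to overall sleep quality. It does not dispose of the point. The premise is a structural feature that the sponsor can settle by looking at its own form, and the missing scoring rule is plain in Section 11.0.

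The second objection is that a 3-point shift is a ceiling. This also stands.

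- The intervention text does not say trazodone is taken every night; daily bedtime use appears in Sections 7.0 and 15.0 as a description of usual hypnotic practice.
- The washout names hypnotics and bedtime sedative antidepressants. Section 1.0 lists over-the-counter medications separately, so their use at baseline is not clearly excluded.
- The documents contain no rule on sleep aids in the CBT arm after entry. Partial adherence, baseline over-the-counter use or CBT-arm use would each shrink the shift.

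The third objection is reach. A reader might infer that the primary subjective outcome is compromised, because Section 2.0 names subjective nighttime sleep as primary and Section 6.0 files the PSQI under that heading. The analysis plan does not support that reading: it analyses the PSQI under the secondary aim and takes diary sleep time as the primary subjective measure. The ISI and the post-sleep questionnaire are also separate measures.

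Finally, replacing a standard score with a modified one would make a pilot less useful for planning later studies. That is a fair point and is met by reporting both.

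**Conclusion.** The point holds as a conditional one. The plan compares PSQI change between an arm assigned a sleep medicine and an arm that is not, and leaves the scoring open. If the total includes a 0-to-3 medicine-use component, assigned trazodone adds between 0 and 3 points to that arm's change. False rejection of the PSQI comparison then rises from 5% to between 8% and 56%, depending on the shift (1 to 3 points) and the assumed SD (3 to 4). The joint test with the ISI rejects in 28% to 62% of trials at the 3-point ceiling, for assumed correlations of 0.3 to 0.6.

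Two stronger readings are tempting and not supported. One is that the comparison is biased by construction by a full 3 points in the trazodone arm alone; the documents establish neither the component, nor nightly use, nor absence of sleep aids under CBT. The other is that the shift could produce a false trazodone success; it works against trazodone and so against the trial's own hypothesis. Sleep duration by polysomnography, actigraphy and diary is not affected. At 9 months the size would depend on whether trazodone continues, which the documents do not state.

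The change should be made, but it concerns one secondary measure of a 24-patient pilot.

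**What to change.** First check the PSQI form used in the trial for a medicine-use component and its weight. If it is there, add to the subjective sleep quality paragraph of Section 11.0, Specific Aim 2, that:

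- the arms are compared, alone and in the joint analysis with the ISI, on the PSQI total without the medicine-use component, scored identically in both arms and at every visit;
- the standard full total and the medicine-use component are also reported by arm.

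If the form has no such component, one sentence stating which PSQI score is analysed is enough.

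The cost is a sentence or two of analysis text and a re-score of data already collected, with no change to visits, treatment or sample size. The small downside is that the reduced total cannot be set against published cut-offs, which is why the full total is still reported. Showing the component by arm also reveals any sleep-aid use under CBT, which the reduced total alone would hide. Fixing the score in advance prevents a choice between versions after the results are known.
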